**Serial no: 0304707**

**9/13/2020**

## **Impact of Zinc to Copper ratio and Lipocalin -2 in Obese Patients Undergoing Sleeve Gastrectomy.**

[name], [name], [name]

Department of Clinical Pathology Alexandria University Hospitals; Department of Surgery  
Alexandria University Faculty of Medicine.

Obesity represents tremendous threat to health globally. WHO conveyed that over 10% of the world's population were classified as obese in 2016, which signifies 3-fold increase in frequency of obesity since 1975. Laparoscopic Sleeve Gastrectomy (LSG) has proved to be an effective procedure for achieving considerable weight loss with significant improvement in obesity-related comorbidities.

A possible role of trace elements in the pathogenesis of obesity has been largely ignored. In particular zinc (Zn) and Copper (Cu) are crucial TE, that act as structural ions in hormones, proteins and receptors and cofactors in various enzymatic reactions. It has been theorized that balance between Zn and Cu has an influence on antioxidant mechanisms and development of associated comorbidities. Nevertheless, few studies have systematically evaluated TE in morbidly obese patients undergoing bariatric surgery.

Lipocalin 2 (Lcn2), also known as NGAL (neutrophil gelatinase-associated lipocalin), Lcn2 is adipokine that belongs to lipocalin family. It is a 25- KD  $\alpha$ -glycoprotein originally identified in human neutrophils. Lcn2 overexpression in adipose tissue stimulates the production of pro-inflammatory cytokine as interleukin 6 (IL-6) and receptor activator of NF- $\kappa$ B ligand.

The aim of the current study primarily was to investigate the value of zinc to copper ratio as possible biomarker of TE imbalance in morbidly obese subjects undergoing LSG. Secondly to correlate it with lipocalin 2 (Lcn2) with respect to Anthropometric measurements and other metabolic markers prospectively.

### **Study design**

### **CONSORT 2010 Flow Diagram**

**Enrollment**

Assessed for eligibility (n= 120 )

## **Materials and methods:**

### **Recruitment**

Morbidly obese subjects attending clinic at Surgery department for laparoscopic sleeve gastrectomy Alexandria University Hospitals.

#### **Pre-assignment Details**

adult morbidly obese subjects were included age above 20 years, BMI above 40

Suffering from comorbidities as hypertension, DM, dyslipidemia.

Assigned participants were clinically evaluated for comorbidities as hypertension, DM, dyslipidemia.

As well as signs of nutritional deficiency as anemia, brittle nails.

### **Group Information**

one group of participants eligible for laparoscopic sleeve gastrectomy were assigned according to their will to participate in study.

#### **Period of evaluation:**

First visit: preoperative for clinical assessment of participants, determine BMI and waist circumference and withdrawal of serum blood sample

Second visit: within one month after surgery to make sure that no complication occurred after surgery.

Third visit: nine months postoperative for revaluation of participants, determine BMI and waist circumference, and withdrawal of a serum blood sample

#### **Number of participants at initiating the period of study.**

They were 120 morbidly obese subjects.

#### **Number of participants at the end of the period of study.**

They were 107 subjects, 13 obese subject withdraw from study as they didn't come during follow up period after 9 months.

Participants according Sex (69 females, and 38 male), with the mean age of  $41.6 \pm 8.9$  years. The mean preoperative BMI was  $47.43 \pm 5.4 \text{ kg/m}^2$ . Then, they were evaluated 9 months after LSG.

### **Preoperative and Postoperative Clinical characteristics and metabolic variables in studied subjects.**

	Preoperative	9 months postoperative	P
Body weight (Kg)	$129.7 \pm 12.1$	$93.4 \pm 13.6$	0.0013*
BMI ( $\text{kg/m}^2$ )	$47.43 \pm 5.4$	$35.7 \pm 3.8$	0.0052*
Waist circumference (cm)	$130.00 \pm 4.68$	$91.82 \pm 3.73$	0.001*

Systolic BP (mmHg)	146.0±17.0	132.0±11.0	0.001*
Total cholesterol (mmol/L)	5.85 ± 0.41	4.64 ± 0.31	0.035*
Triglycerides (mmol/L)	2.20 ± 0.23	1.92 ± 0.24	0.106
HDL cholesterol (mmol/L)	1.23 ± 0.19	1.39 ± 0.2	0.041*
LDL cholesterol (mmol/L)	3.37 ± 0.23	2.97 ± 0.21	0.022*
HOMA-IR	2.64 ± 1.3	1.44 ± 0.81	0.013*
S. Leptin (ng/ml)	102.87 ± 49.16	33.47 ±12.76	0.0001*
CRP (mg/L)	8.4±5.91	3.2±2.98	0.001*
Lipocalin 2 (µg/L)	107.24±36.8	51.6±12.73	0.001*
Albumin (g/dl)	4.05±0.21	3.91±0.29	0.113

\*Statistically significant at (p≤0.05).

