### **Statistical analysis**

All data will be analyzed with Statistical Package for the Social Sciences version 20 software (SPSS, Inc., Chicago, IL). Results will be displayed as mean  $\pm$  SD. Paired Student's t-test used to compare the data pre-operative and nine months postoperative. The chi-squared test used for category variables. Spearman correlation coefficient used to detect the correlation between different variables. Statistical correlations calculated by Pearson's correlation test.  $P < 0.05$  is considered significant.

[name]

Consultant Clinical Pathology at Alexandria University Hospitals

Alexandria University, Faculty of Medicine Alexandria University Hospitals

Mobile [contact]

Faculty contact no: [name]

Email: [contact]

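### At least 8 of the 13 p-values in the pre/post table cannot come from a paired t-test on 107 pairs with the printed means and SDs

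*Combined protocol and SAP*

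**What the plan says.** The Statistical analysis section names the test: "Paired Student's t-test used to compare the data pre-operative and nine months postoperative". It also defines the format, "Results will be displayed as mean" with the SD after the ± sign. The section on participants at the end of the study gives the number followed: "They were 107 subjects, 13 obese subject withdraw from study as they didn't come during follow up period after 9 months".

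The table of preoperative and postoperative characteristics has 13 rows, each with two means, two SDs and a p-value. It gives no n per row. Its footnote marks p at or below 0.05 with an asterisk. Eleven rows carry the asterisk. The two that do not are "Triglycerides (mmol/L) 2.20 ± 0.23 1.92 ± 0.24 0.106" and "Albumin (g/dl) 4.05±0.21 3.91±0.29 0.113". Among the marked rows is "Total cholesterol (mmol/L) 5.85 ± 0.41 4.64 ± 0.31 0.035".

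**The concern.** Several printed p-values are far too large for the changes beside them. Total cholesterol falls by 1.21 mmol/L against SDs of 0.41 and 0.31, which is several SDs, yet p is 0.035. Triglycerides fall by more than one SD in about 107 people, yet p is 0.106.

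Two things are at stake. First, the two rows labelled not significant may be mislabelled. Second, if the p-values disagree with the means, SDs and n, a reader cannot tell which column to trust. If the SDs are the faulty part, the spread reported for those variables is wrong as well.

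**Working it through.** **Inputs.** Means, SDs and p-values come from the table. The number of pairs is n = 107, from the section on participants at the end of the study. The test and the meaning of ± come from the Statistical analysis section. Sidedness is not stated, so I take the test as two-sided; a one-sided test would halve every p below.

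**Formula.** For a paired t-test, t = |m1 − m2| / (SDdiff/√n) on n − 1 = 106 df. SDdiff depends on the pre/post correlation r, which is not reported:

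SDdiff² = s1² + s2² − 2·r·s1·s2

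This is largest at r = −1, where SDdiff = s1 + s2. That gives the smallest possible t and the largest possible p, so no value of r has to be assumed.

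**Trying to reproduce the triglyceride value.** The difference is 2.20 − 1.92 = 0.28, and the largest SDdiff is 0.23 + 0.24 = 0.47.

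- Smallest t = 0.28 / (0.47/√107) = 0.28/0.0454 = 6.16, so p is at most 1.3e-8. The printed value is 0.106.
- Working backwards, p = 0.106 on 106 df needs t = 1.63, so SDdiff = 0.28 × √107 / 1.63 = 1.78. That is 1.78/0.47 = 3.8 times the maximum.

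**The eight rows that fail.** The last column is the largest number of pairs, at r = −1, for which p is still at or above the printed value.

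| Row | Difference | s1 + s2 | Smallest t | Largest possible p | Printed p | SDdiff needed ÷ maximum | Largest n giving printed p |
|---|---|---|---|---|---|---|---|
| Weight | 36.3 | 25.7 | 14.61 | 3.8e-27 | 0.0013 | 4.4 | 10 |
| BMI | 11.73 | 9.2 | 13.19 | 4.3e-24 | 0.0052 | 4.6 | 8 |
| Total cholesterol | 1.21 | 0.72 | 17.38 | 8.3e-33 | 0.035 | 8.1 | 4 |
| Triglycerides | 0.28 | 0.47 | 6.16 | 1.3e-8 | 0.106 | 3.8 | 9 |
| HDL | 0.16 | 0.39 | 4.24 | 4.7e-5 | 0.041 | 2.1 | 27 |
| LDL | 0.40 | 0.44 | 9.40 | 1.2e-15 | 0.022 | 4.0 | 9 |
| HOMA-IR | 1.20 | 2.11 | 5.88 | 4.8e-8 | 0.013 | 2.3 | 22 |
| Albumin | 0.14 | 0.50 | 2.90 | 0.0046 | 0.113 | 1.8 | 33 |

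The other five rows (waist, systolic BP, leptin, CRP, lipocalin 2) are printed as 0.001 or 0.0001. Their maxima run from 9e-73 to 1.1e-6, so those values cannot be exact either. They may be thresholds that lost a "<" sign, so I do not count them.

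**Other explanations tried.**

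- *Rounding.* With every printed value rounded in the least favourable direction, the largest p is 6.4e-8 for triglycerides, 0.0007 for HDL and 0.0096 for albumin. The SDdiff ratios become 1.65 to 7.9.
- *Unpaired t-test, 107 per time point.* Triglycerides 8.5e-16, albumin 7.3e-5.
- *n = 120.* p falls further: triglycerides 1.7e-9, albumin 0.0027.
- *± read as SE.* The preoperative weight SD would be 12.1 × √107 = 125 kg, and the plan says SD.
- *SDs used as if they were SEs when p was computed.* This could give some rows at a plausible correlation (triglycerides about 0.73, LDL 0.70, BMI 0.65, weight 0.64). Total cholesterol would need −0.22, albumin 0.99 and HOMA-IR slightly above 1, so it does not explain the whole column.

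**Effect on the two labels.** The widest possible 95% CI is the difference ± t(0.975, 106 df) × (s1 + s2)/√107. It runs from 0.19 to 0.37 mmol/L for the triglyceride fall and from 0.04 to 0.24 g/dl for the albumin fall. Both exclude zero. At r = −1, triglycerides are significant from 14 pairs and albumin from 52 (15 and 62 with worst-case rounding).

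**The case against.** The strongest objection is that the table does not say both columns describe the same 107 people. The study started with 120, and if the preoperative column used all of them, s1 + s2 is no longer a strict bound for the pairs. In the extreme case, with all 13 dropouts at one identical value and correlation −1, the largest albumin p rises to about 0.050, or 0.10 with worst-case rounding. Triglycerides reach 2.6e-7, HDL about 0.001 and HOMA-IR about 2e-6. None reaches its printed p. The case is artificial, and the section that reports the 107 completers gives the same preoperative BMI (47.43 ± 5.4) as the table. What stands is that the albumin label is less secure than the triglyceride label.

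Missing assays cannot be strictly excluded, because no n per row is given. Albumin would need 33 or fewer pairs and HDL 27 or fewer, which is less absurd than 4 for total cholesterol. But no such loss is reported, no single n fits the column, and weight and BMI are not assays.

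The table itself names no test. The fault may lie there, though an unpaired t-test fails too.

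On importance, the primary outcome is not in the table, 11 labels are unchanged, and the label changes are unadjusted for multiplicity. No adjustment is planned, but a factor of 13 would take the albumin bound to 13 × 0.0046 = 0.06. These points limit the consequence. They do not remove the need to correct eight printed values.

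**Conclusion.** The concern holds. Eight of 13 printed p-values exceed the mathematical maximum for the stated test with the printed means, SDs and 107 pairs, for every possible correlation and after worst-case rounding. The count is conservative, since it leaves out the five rows that may be truncated.

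Two of 13 labels (triglycerides and albumin) change to significant on condition that the printed means, SDs and n are right, with p unadjusted and two-sided. The result assumes that all 107 pairs enter each row and that both columns describe the same people. The documents do not show which of the p-values, SDs, n per row or test is wrong, and no cause is asserted here.

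**What to change.** Re-run the paired t-test for every row from subject-level data. For each row report the number of complete pairs, the mean paired change, its 95% CI and p (as p<0.001 where that applies), and state in the table that ± is SD. Correct whichever of the p-values, SDs, n or named test proves wrong. Restate triglycerides and albumin as statistically significant falls only if the printed means, SDs and number of pairs are confirmed.

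The cost is one SPSS re-run and a corrected table with an n column. No new data are needed.

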#### **Outcome measures:**

primarily was to investigate the value of zinc to copper ratio as possible biomarker of TE imbalance in morbidly obese subjects undergoing LSG.

For detection of presence of micronutrient deficiency in morbid obesity in form of zinc to copper ratio and re-evaluate it after loss of weight

Secondly to correlate it with lipocalin 2 (Lcn2) with respect to Anthropometric measurements and other metabolic markers prospectively.

As zinc to copper ratio is considered as biomarker of micronutrient status; therefore, correlate it with other biomarkers of inflammation (lipocalin 2) and other parameters as BMI, FBG to determine if micronutrient status improve after weight loss or not

**Time frame:** 9 months.

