#### **Follow-up and outcome parameters:**

All studied subjects will be followed up for early postoperative complications (within the first month) as Bleeding or Leak. Then they will be reviewed after 9 months postoperatively for assessment of anthropometric measurements, control of preoperative comorbidities, and manifestations of TE deficiencies (anemia, hair loss, teeth problems, edema. etc.).

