### **Biochemical parameters**

Fasting blood samples will be collected from participants prior to surgery and nine months postoperative, after overnight fast and divided into two tubes; EDTA for complete blood count, the rest into plastic tubes and serum sample.

Serum glucose and Total cholesterol, HDL- cholesterol, LDL- cholesterol, and triglyceride, total protein and Albumin. Serum iron (Fe), and ferritin.

Serum insulin, Ceruloplasmin, Zn and Cu levels, CRP and lipocalin-2 (Lcn2) .

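### The zinc-to-copper ratio suits a question of balance, but alone it cannot show deficiency or improvement in micronutrient status; those statements should rest on serum zinc and copper separately

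*Combined protocol and SAP*

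**What the plan says.** The primary aim, given in the introduction and again under Outcome measures, is to study "the value of zinc to copper ratio as possible biomarker of TE imbalance". Outcome measures then adds two further uses of the same ratio:

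- Deficiency: "For detection of presence of micronutrient deficiency in morbid obesity in form of zinc to copper ratio and re-evaluate it after loss of weight".
- Status: "As zinc to copper ratio is considered as biomarker of micronutrient status", the plan is to "correlate it with other biomarkers of inflammation (lipocalin 2) and other parameters as BMI, FBG", the purpose being "to determine if micronutrient status improve after weight loss or not".

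The separate levels are collected. Biochemical parameters provides for fasting samples before surgery and at nine months, and lists "Serum insulin, Ceruloplasmin, Zn and Cu levels, CRP and lipocalin-2 (Lcn2" as well as "Serum iron (Fe), and ferritin". The section headed "Follow-up and outcome parameters" has clinical signs of trace-element deficiency reviewed at nine months, and Pre-assignment Details has signs of nutritional deficiency assessed at entry.

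Statistical analysis applies a paired t-test to the data before surgery and at nine months, a chi-squared test to categorical variables, and Spearman and Pearson correlations. No section gives a deficiency limit for zinc, copper or the ratio, and none ties the deficiency or improvement conclusion to the separate levels.

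**The concern.** Imbalance is a question about one element relative to the other, and a ratio answers it. Deficiency and improvement in status are questions about level. Outcome measures uses the ratio for both kinds of question without saying that the second kind needs the components.

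Two routes lead from the ratio to a conclusion on status: comparing it before and after weight loss, and correlating it with lipocalin 2, BMI and FBG. Neither recovers the levels once they have been divided out, and none of the three correlates is itself a zinc or copper level. A report that follows the wording could state that deficiency was present, or that status improved, without showing whether either element was low before surgery or fell after it. The separate paired comparisons might show this, but the plan does not say that the conclusion rests on them.

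**Working it through.** The documents give no zinc, copper or ratio value, and no power or threshold figure on this point, so there is no stated figure to reproduce. The check is algebra, with illustrative values marked as assumed. Write R = Zn/Cu.

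**1. A shared proportional change cancels.** For any k > 0, (k × Zn)/(k × Cu) = Zn/Cu. Assumed pairs 100/100, 70/70 and 50/50 all give R = 1.000. This holds with a different k for each patient. Each patient's R is then unchanged, so Pearson and Spearman correlations of R with lipocalin 2, BMI or FBG are unchanged too. No distributional assumption is needed.

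**2. One ratio, several level patterns.** Assumed pairs, read against a reference pair of 100/100:

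- 70/98 = 0.714: zinc 30% lower, copper nearly unchanged.
- 100/140 = 0.714: zinc unchanged, copper 40% higher.
- 130/182 = 0.714: both higher.

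A low ratio therefore does not say which element is out of range, or in which direction.

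**3. Direction of change.** Change in R = (1 + dZn)/(1 + dCu) − 1. With assumed changes:

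- Zn −12.5%, Cu −25%: 0.875/0.75 = 1.167, so +16.7% while both fall.
- Zn +16.7%, Cu unchanged: 1.167/1 = 1.167, so +16.7% while zinc rises.
- Both −10%: 0.9/0.9 = 1, so 0%.
- Both −20%: 0.8/0.8 = 1, so 0%.

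**4. How far the ratio can track level.** Assume that log Zn and log Cu are bivariate normal with equal SD and correlation rho. The correlation of log R with log Zn is (1 − rho)/√(2(1 − rho)) = √((1 − rho)/2). That is √0.65 = 0.81 at rho = −0.3 and √0.05 = 0.22 at rho = 0.9. In a simulation with low defined as the lowest 10% of each element, the AUC of a low ratio for low zinc ran from 0.92 to 0.62 over that range. For both elements low, and for either low, it was about 0.50 throughout. The 0.50 reflects the symmetry assumed between the elements and a ratio read in one direction only, so it is an illustration and not an estimate.

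**5. Is the alternative informative at this size?** The document reports 120 at the start and 13 lost, so 120 − 13 = 107 pairs at most. If all 120 have a preoperative sample, the Wilson 95% CI for an assumed prevalence below the limit is:

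- 12/120 = 10%: 5.8% to 16.7%.
- 24/120 = 20%: 13.8% to 28.0%.

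These intervals describe the precision of the proposed result. They do not measure the size of the defect.

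**The case against.** The strongest reply is that the fault is mostly one of wording. The introduction states the aims as imbalance and correlation and does not mention detecting deficiency, so the deficiency phrase may be a loose restatement of imbalance. Zinc and copper are measured separately at both visits, the paired t-test is worded widely enough to cover them, and clinical signs of deficiency are reviewed. All of this is correct, and it keeps the point small. It does not remove it: the outcome text makes the ratio the form in which deficiency is detected, and nothing ties the conclusion to the levels or the signs.

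A reader might infer four stronger things that the documents do not support:

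- That the ratio carries no information on level. It may partly track zinc, as step 4 shows under its assumptions, and the documents give no joint distribution that would settle how far.
- That its correlations stay the same whatever the levels do. That holds only for a proportional change common to both elements; unequal changes move the ratio.
- That improvement is to be judged by correlation alone. The text also provides for re-evaluating the ratio after weight loss.
- That zinc and copper levels are missing from the study. They are collected; what is missing is their place in the conclusion.

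**Conclusion.** The point holds in a limited form. Using the ratio for trace-element imbalance is sound. Using it to detect deficiency, or to decide whether status improved, is not, because the ratio alone cannot identify the level of either element. That conclusion rests on the algebra in steps 1 to 3 and needs no assumption about distributions; the percentages there are assumed examples.

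The size or likelihood of a misreading cannot be estimated. The results table covers 13 variables, and none is zinc, copper or the ratio. For the same reason, a reader should not infer that a wrong conclusion has been drawn: nothing in the documents shows one. It is worth correcting because it concerns the study's lead measure and can be corrected with values already planned.

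**What to change.** In Outcome measures:

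1. Limit conclusions from the ratio to zinc-copper balance.
2. Base any statement on deficiency or improvement on serum zinc and serum copper separately. For each, give the mean paired change with 95% CI and the proportion below the laboratory's own stated reference limit at each visit. Report preoperative prevalence on everyone with a preoperative sample (up to 120) and change on pairs (up to 107).
3. Compare the paired proportions with a paired method such as McNemar's test. The only categorical test in Statistical analysis is the chi-squared test, and its form for independent groups would ignore that the same patients are measured twice.
4. Nine-month results for other variables are already in the document, and it does not show whether the zinc and copper data have been seen. If they have, label these analyses post hoc.

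Cost: no new samples or visits. The additions are 4 proportions (2 elements × 2 visits) and 2 paired comparisons of proportions, plus 2 mean paired changes that the planned t-test can already cover. The laboratory's reference limits must be stated, since the documents do not give them. The downside is a few more reported results, possibly post hoc, and a more restrained conclusion.

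### No planned analysis can show that the preoperative Zn/Cu ratio is abnormal, so the detection half of the primary outcome is unsupported; the before-after half is not affected

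*Combined protocol and SAP*

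**What the plan says.** All references are to the combined protocol and SAP.

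- **Outcome measures.** The primary aim is given as "primarily was to investigate the value of zinc to copper ratio as possible biomarker of TE imbalance in morbidly obese subjects undergoing LSG". The next sentence spells it out: "For detection of presence of micronutrient deficiency in morbid obesity in form of zinc to copper ratio and re-evaluate it after loss of weight". The first part is about the state before surgery; the second is about what happens to the ratio afterwards.
- **Group Information.** "one group of participants eligible for laparoscopic sleeve gastrectomy were assigned according to their will to participate in study".
- **Pre-assignment Details.** "adult morbidly obese subjects were included age above 20 years, BMI above 40".
- **Biochemical parameters.** "Fasting blood samples will be collected from participants prior to surgery and nine months postoperative". Zn and Cu are on the list of serum measurements. No reference interval or cut-off is given for either, or for their ratio.
- **Statistical analysis.** "Paired Student's t-test used to compare the data pre-operative and nine months postoperative". The section also lists means with SD, a chi-squared test for categorical variables, and Spearman and Pearson correlations. It names no categorical version of the ratio and no test against a reference value.

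**The concern.** To say that a ratio detects deficiency or imbalance in morbid obesity, one must know which values count as deficient or imbalanced. That needs a non-obese comparator, a reference interval, a cut-off, or an independent definition of deficiency against which the ratio is judged. The plan specifies none of these. The only contrast it offers for the preoperative ratio is the same patients' ratio 9 months after sleeve gastrectomy.

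At stake is the first half of the headline claim. If the plan is followed as written, the study will report a change in the ratio and some correlations, and a conclusion about deficiency in morbid obesity would have no analysis behind it.

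**Working it through.** The plan gives no sample-size, effect-size or SD figure for the ratio, so there is no figure of its own to reproduce. The check has three parts.

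**1. What each planned analysis can say about the preoperative level**

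Write R0 for a patient's ratio before surgery and R9 for the ratio at 9 months.

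- *Paired t-test.* It uses only D = R9 − R0. Add any constant c to every value at both visits: (R9 + c) − (R0 + c) = D. The t statistic and P value are unchanged. A cohort with normal ratios at both visits and one with abnormal ratios at both visits can therefore give the same result.
- *Pearson and Spearman correlations.* Both are also unchanged when a constant is added to the ratio. They show association with lipocalin 2 or BMI, not whether the ratio is abnormal.
- *Chi-squared test.* It could compare deficient with non-deficient patients, but only after a category is defined, and none is.
- *Mean and SD.* The preoperative mean does describe level, but the plan gives nothing to compare it with.

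**2. Whether the 9-month value could serve as the reference**

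Inputs, from the table of preoperative and postoperative characteristics: BMI 47.43 ± 5.4 before and 35.7 ± 3.8 at 9 months; weight 129.7 kg before and 93.4 kg at 9 months. Assumptions: BMI is normally distributed at 9 months, and obesity means BMI 30 or above (the documents give no such cut-off).

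- With the printed mean: z = (30 − 35.7)/3.8 = −1.50, so P(BMI ≥ 30) = 93.3%.
- The printed weights imply a slightly lower mean. Height squared is about 129.7/47.43 = 2.735 m², so BMI at 9 months is about 93.4/2.735 = 34.2. This uses a ratio of means, so it is approximate. Keeping the SD at 3.8, z = (30 − 34.16)/3.8 = −1.09, so P(BMI ≥ 30) = 86.3%.
- Below an assumed cut-off of 25: z = (25 − 35.7)/3.8 = −2.82, or 0.24%, with the printed mean; about 0.8% with 34.2.

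On either mean, the 9-month sample is mostly obese. It is also taken after the operation, so the operation and the weight loss are not separated.

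**3. What the available numbers would support**

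"They were 120 morbidly obese subjects" at the start; 107 were seen at 9 months, so 13/120 = 10.8% were lost.

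- *Change.* At two-sided 0.05 and 80% power (both assumed), the paired test on 107 patients can detect (1.960 + 0.842)/√107 = 0.27 SD of the within-patient difference. The re-evaluation limb is workable.
- *Proportion outside a reference interval.* The 95% CI half-width is 1.96 × √(p(1 − p)/n). With n = 120 before surgery it is 5.4 percentage points at p = 10% and 8.9 at p = 50%. With n = 107 at 9 months it is 5.7 and 9.5.

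**The case against.** A reader might infer that the study cannot meet its primary aim at all. The documents do not support that. The aim has two limbs, and a within-patient comparison is a proper way to describe the second.

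A reader might also infer that the plan treats the 9-month value as normal, so that a rise would count as proof of earlier imbalance. No section says so. The Outcome measures section speaks of whether micronutrient status improves after weight loss, which is a statement about change. The BMI figures above show only that the 9-month value could not fill the gap if someone tried to use it so. They describe BMI, not the ratio: the table prints no Zn, Cu or Zn/Cu values, so the effect on the primary outcome itself cannot be quantified.

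Nor does the plan rest on the paired test alone. It lists other tests. Clinical signs of deficiency are assessed (Pre-assignment Details; Follow-up and outcome parameters), and ceruloplasmin, iron, ferritin, albumin and a blood count are measured (Biochemical parameters). These could have served as internal anchors for an abnormal ratio. This part of the objection stands as to data collected, but no analysis links any of them to the ratio, so the detection limb remains without support.

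Lastly, one may say that the gap is a missing definition and not a flaw of the single-group design. That is largely right: a control arm is not required, and an interval applied to values already measured would suffice. Yet more than detail is missing, because without that definition no listed analysis addresses the first limb.

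**Conclusion.** The concern holds for the detection limb of the primary outcome and not for the re-evaluation limb. As written, the plan yields a change in the ratio and correlations, neither of which can show that the preoperative ratio was abnormal. That conclusion follows from the form of the planned tests and needs no distributional assumption.

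That the 9-month value is not a normal-weight reference rests on about 86% to 93% of patients remaining at BMI 30 or above. This assumes normality, a cut-off of 30, an SD of 3.8, and a mean of 34.2 (implied by the weights) or 35.7 (printed). The conclusion is the same across that range.

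A change in the ratio may fairly be described as occurring after weight loss, since that is its timing. It cannot be attributed to weight loss as distinct from the operation.

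**What to change.** 1. Before the ratio is analysed, fix an existing laboratory reference interval for Zn/Cu obtained by the same method, or intervals for Zn and Cu separately. Report the proportion of patients outside it, with 95% CI, preoperatively and at 9 months. The protocol already reports completed follow-up and P values for other variables. If the ratio has been analysed too, say that the interval was chosen afterwards.
2. If no valid interval exists, restate the primary outcome as the change in serum Zn/Cu ratio from before to 9 months after sleeve gastrectomy, and drop the claim to detect deficiency or imbalance in morbid obesity.
3. In either case, describe the change as following the operation and its weight loss, without attributing it to weight loss alone.

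Cost: a wording change and one descriptive analysis of values already measured, with no new patients and no new assays. The downside is a narrower primary claim if no valid interval exists.
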